### Study Drug

Blinded study drug bottles will be packaged, labeled and shipped from a contracted pharmacy (Belmar Pharmacy, Lakewood, CO) based on sequence number. Sildenafil and placebo will be stored and dispensed through the research pharmacy at NJH. An accurate accounting of dispensing and return of the study drug will be maintained by the research pharmacist at each institution.

### Patient reimbursement

In accordance with TDN guidelines, patients will be reimbursed according to the following schedule:

Visit	Visit 1	Visit 2	Visit 3	Visit 4	Visit 5	Total
Payment	\$75	\$200	\$200	\$200	\$25	\$700

Subjects who complete the screening visit, will receive the \$75 payment regardless of whether they qualify for the study to compensate for their time and effort.

Subjects who live greater than 50 miles from the study site, will be reimbursed at the current standard mileage rate for medical purposes.

## Statistical analysis

### Sample size

Using PASS 13, data from two consecutive within subject NPD measurements following treatment with placebo in a trial of the Na transport inhibitor QAU145 were used to perform power calculations for this study. Based on a 2.59 mV standard deviation of the change in conductance of the maximal basal PD with placebo, enrollment of 12 (sildenafil) and 6 (placebo) subjects will provide 100% power to detect a 10.4 mV change in maximal basal PD at the 5% significance level. The reported results from the VX-770-101 trial reported at NACFC in 2008 also indicate that this study is well-powered to detect changes in sweat chloride. Based on a standard deviation of 2.6 mEq, enrollment of 12 (sildenafil) and 6 (placebo) subjects will provide 95% power to detect at least a 5 mEq change from placebo at the 5% significance level.

### Data Analysis

Primary outcome, baseline change in maximal basal PD measurement (mean of 2 nostrils), will be assessed as well as change with amiloride and total change in PD. Secondary outcomes include the mean basal PD, end Ringer's perfusion PD, change with amiloride, change with low chloride, change with isoproterenol, change with low chloride plus isoproterenol, and total change in NPD (delta NPD). Analysis of NPD results will be performed at the Center for CFTR Detection at UAB. All NPD tracings will be interpreted by an independent, blinded investigator, and no scoring will be conducted by the site investigator to prevent biased estimates. All tracings will be scored with electronic assisted data analysis (developed by the UAB Center for CFTR detection). Data for both the primary and the secondary endpoints (other Na and Cl conductance measures by NPD and the concentration of Na and Cl in sweat) will be analyzed separately as a 2X2 crossover design using a repeated measures analysis.

If emerging data from ongoing CFTR modulator trials and NPD measurements obtained using the latest NPD methodology suggests alternative analytic methods (including log transformation) should be used, statistical analysis methods will be updated prior to data base lock and analysis initiation. If these analysis suggests non-normality, rank based analyses (e.g. Mann-Whitney-Wilcoxon rank-sum test or other appropriate test) will be used. Any change in the statistical analysis plan will be finalized before database lock, and reported to the DSMB and CF-TDN PRC. Data will be also be presented using descriptive analyses including individual patient line plots of outcome over time. All patients will be plotted across part one and part two to discern carryover effects.

Data from pharmacokinetic analysis will be analyzed using ANOVA in SAS v.9.2. P-values  $\leq 0.05$  will be regarded as significant. Data will be screened for nonnormality, and appropriate transformations as needed (such as log) will be applied; careful residual analysis will be performed to detect outliers and other anomalies. Non-parametric procedures (Proc NPAR1WAY in SAS v9.2) will be applied in cases where transformations do not normalize the data. Carryover effects in the crossover design will be fit initially but discarded if they are not (as expected) significant. Correlations between NPD, sweat chloride and clinical parameters will also be conducted. All statistical analysis will be performed in conjunction with [name] and CCTSI statisticians.

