**Aim 3. Further evaluate the safety and tolerability of sildenafil in subjects with CF**

- a. Evaluate the effect of sildenafil on treatment emergent adverse events
- b. Evaluate the effect of sildenafil on change in clinical laboratory measures, vital signs and physical exam findings

Primary Endpoints

Na+ conductance by nasal potential difference (within subject change in maximum basal PD)

Secondary Endpoints

Other measures of Na transport (mean basal PD, end-ringers profusion PD, change in PD with amiloride)  
 Cl conductance by NPD (total Cl conductance, change in PD with chloride free solution, change in PD with isoproteronol, total change in NPD (delta NPD))  
 Sweat Na+ by pilocarpine iontophoresis  
 Sweat Cl concentration by pilocarpine iontophoresis  
 Pulmonary function by spirometry  
 Lung clearance index  
 Exhaled nitric oxide (eNO)  
 Sputum nitric oxide metabolites  
 Safety and tolerability (including laboratory studies, CFQ-R)

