Subjects will be randomized in a 2:1 fashion to sildenafil or placebo. The randomization protocol will be created by [name] (Professor and Head, Division of Biostatistics and Bioinformatics, National Jewish Health). The protocol will be provided directly to the study pharmacist, who will communicate randomization to the coordinator at the research site.

Dosing

During the course of the study, patients will receive 4 weeks of therapy: 28 days of placebo orally t.i.d. or 28 days of days of sildenafil orally t.i.d. Dosing of sildenafil will be escalated weekly (20 mg orally t.i.d for the first week, 40 mg orally t.i.d. for the second through fourth weeks.) Patients receiving placebo will have sham dose escalation to maintain blinding. Patients not tolerating dose escalation will be discontinued from the study.

Screening visit (visit 1; Day -14-0):

Prior to conducting any study-related activities, written informed consent/assent will be obtained, signed and dated by the subject and/or parent/guardian.

A medical history including diagnosis of CF, current medications and other relevant past medical history will be obtained, and a complete physical exam will be performed by the principal investigator including nasal exam rating (NER), height, weight, temperature, blood pressure, respirations and baseline pulse oximetry will be recorded. Any abnormal findings will be documented. Clinical laboratory tests will be performed including CBC with differential, chemistry profile, INR (total of 10cc of blood), and a urine pregnancy test (for females of child-bearing potential). A baseline EKG will be obtained. Subjects will undergo spirometry according to ATS criteria.

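### No baseline adjustment is specified for the between-arm NPD and sweat comparisons, although Visit 2 values are scheduled for every subject

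*Combined protocol and SAP*

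**What the plan says.** Under Primary Endpoints, the primary is the "within subject change in maximum basal PD". The Data Analysis section repeats it: "baseline change in maximal basal PD measurement (mean of 2 nostrils), will be assessed".

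The Sample size section works on the same scale. It is "Based on a 2.59 mV standard deviation of the change in conductance of the maximal basal PD with placebo" and claims "100% power to detect a 10.4 mV change in maximal basal PD". For sweat chloride, "Based on a standard deviation of 2.6 mEq", it states that "enrollment of 12 (sildenafil) and 6 (placebo) subjects will provide 95% power to detect at least a 5 mEq change from placebo".

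Under Randomization, "Subjects will be randomized in a 2:1 fashion to sildenafil or placebo"; the Dosing section then gives each subject a single 28-day course of one or the other. No stratification factor is named.

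The Visit 2 description and the study flowchart schedule NPD and sweat testing for every subject, and the visit description lists both before the first dose. They are repeated at Visit 3 (Day 8) and Visit 4 (Day 29).

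The Data Analysis section assigns the NPD and sweat endpoints to a two-period crossover analysis with repeated measures, and adds carryover terms. Its fallback is a rank-based test. Neither the main model nor the fallback mentions the baseline value as a covariate.

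**The concern.** A raw change score fixes the coefficient of the baseline at one. If the correlation between baseline and follow-up is below one, and the SDs are similar at the two visits, subtraction over-corrects: a subject who starts high by chance tends to fall back whatever the treatment. With 12 against 6 subjects and no stratification, a sizeable chance difference in baseline is ordinary, and an unadjusted change comparison passes part of it into the estimated treatment effect.

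The data needed to deal with this are already scheduled, so what is missing is a statement of how they will be used. At stake are the width of the confidence intervals, the power for effects smaller than the planned one, and how far the estimate from this one small allocation can be explained by where the two arms started. Naming the adjustment in advance also removes a choice between adjusted and unadjusted results after unblinding.

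**Working it through.** **Inputs from the Sample size section.** SD of the change in maximal basal PD 2.59 mV; effect 10.4 mV; sweat chloride SD 2.6 mEq (not said whether of a change or of a level) and effect 5 mEq; 12 and 6 subjects; 5% level (sidedness not stated).

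**Assumptions.** The baseline to follow-up correlation ρ is not in the documents and is shown as a range. Equal SDs at both visits, normal data, one follow-up time. The 2.59 mV comes from placebo subjects in another trial and is taken at face value.

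**1. The plan's own figures.** The standard error of the arm difference is SD × √(1/12 + 1/6) = SD × 0.5.
- PD: 2.59 × 0.5 = 1.30 mV. A two-sided t test on 16 df gives 100.0% power for 10.4 mV.
- Sweat chloride: 2.6 × 0.5 = 1.30 mEq. The same test gives 95.0% for 5 mEq.

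Both stated figures reproduce. The sweat figure is the informative one: a normal approximation gives 97.0% and a one-sided t test 97.9%. The sample size therefore matches an unadjusted two-sided two-sample t test.

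**2. Adjusted against raw change.** With single-visit SD σ, the variance of change is 2σ²(1 − ρ) and the residual variance after regression on baseline is σ²(1 − ρ²). Their ratio is (1 + ρ)/2. Estimating the slope with N = 18 multiplies the variance by 1 + 1/(N − 4) = 15/14. So

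variance ratio = (1 + ρ)/2 × 15/14.

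Break-even is at (1 + ρ)/2 = 14/15, that is ρ = 13/15 = 0.87. As ρ nears 1 the ratio tends to 15/14, or +7%.

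**3. Effect of a chance imbalance.** Given an observed baseline difference, the raw-change estimate shifts by −(1 − ρ) times that difference. With the SD of change fixed, σ = 2.59/√(2(1 − ρ)), and the standard error of the baseline difference is 0.5σ. At ρ = 0.5, σ = 2.59 and the shift is 0.5 × 0.5 × 2.59 = 0.65 mV, half the estimate's own standard error of 1.30 mV.

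**4. Results.** The PD effect with 80% unadjusted power is 3.86 mV. This is an illustrative effect, not a planned one. The sweat column takes 2.6 mEq as an SD of change; the unadjusted power there is 95.0%.

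| ρ | σ (mV) | Variance ratio | Shift per 1-SE imbalance (mV) | Adjusted power, 3.86 mV | Adjusted power, sweat 5 mEq |
|---|---|---|---|---|---|
| 0.3 | 2.19 | 0.70 | 0.77 | 92% | 99.0% |
| 0.5 | 2.59 | 0.80 | 0.65 | 87% | 98.0% |
| 0.7 | 3.34 | 0.91 | 0.50 | 83% | 96.4% |
| 0.85 | 4.73 | 0.99 | 0.35 | 80% | 95.0% |
| 0.9 | 5.79 | 1.02 | 0.29 | 79% | 94.5% |

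At 10.4 mV the adjusted power is about 100% in every row.

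**5. Simulation check** (40,000 trials each at ρ = 0.3, 0.5, 0.7 and 0.9). Variance ratios were 0.69, 0.81, 0.91 and 1.02. The slope of the raw-change estimate on the baseline difference was −0.70, −0.50, −0.31 and −0.10. The mean error was essentially zero, and the type I error of the raw-change test was 4.9% to 5.2%.

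**6. If follow-up alone were compared.** The sweat endpoints are described as concentrations, so this reading is open. The ratio is then (1 − ρ²) × 15/14: 0.98, 0.80, 0.55 and 0.20 at ρ = 0.3, 0.5, 0.7 and 0.9. Adjustment gains most over this comparison where it gains least over raw change.

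**The case against.** The strongest reply is that the analysis section never states a t test on change. It states a crossover repeated-measures model, and the documents leave open whether Visit 2 would enter as a repeated response, by subtraction or not at all. Entered as a response, it could recover most of the gain. On this view the real defect is the crossover model, and baseline handling belongs to that repair. The first half stands: the model does not fit a parallel design and must be replaced in the same edit. But removing the crossover alone would leave a change endpoint, sized by an unadjusted test, with no stated role for the Visit 2 value.

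The gain is also uncertain, and this stands in full. At ρ = 0.3 the implied single-visit SD is 2.19 mV, so the planned 10.4 mV would be nearly five such SDs (10.4/2.19 = 4.7). The inclusion criteria admit subjects both on and off Orkambi. If that widens the spread between subjects while the SD of change stays fixed, ρ rises and the gain shrinks.

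Three stronger readings are tempting, and the documents support none of them.
- A reader might infer that all NPD and sweat endpoints are analysed as change from baseline. Only the primary is so described. Sweat is listed as a concentration, and items such as the change with amiloride are changes within one NPD test.
- A reader might infer bias or an inflated error rate. Unadjusted change is unbiased over randomisation, with type I error of about 5%; the shift in step 3 is conditional on the imbalance observed.
- A reader might infer that the trial is underpowered without adjustment. For 10.4 mV it is not: a 0.65 mV shift is about 6% of that effect.

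**Conclusion.** The point holds as a gap in specification with a conditional efficiency cost. No baseline adjustment is named for the between-arm NPD and sweat comparisons, the baseline is scheduled for everyone, and the stated model cannot be applied to the parallel design.

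For the primary, adjustment lowers the variance by 30% at a correlation of 0.3 and by 9% at 0.7, breaks even at about 0.87, and costs at most about 7% as the correlation nears 1. These figures rest on equal SDs, a single follow-up time and a correlation that the documents do not supply, so it cannot be said outright that precision is lost. The benefit is narrower intervals and better power for smaller effects if the correlation is below about 0.87, together with protection against chance imbalance between 12 and 6 subjects. The change is worth making, but the planned primary test does not depend on it.

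**What to change.** In the Data Analysis section, replace the crossover model, and with it the carryover text, by a parallel-group linear model for each NPD and sweat endpoint containing treatment arm and the subject's own Visit 2 value of that measure. If Days 8 and 29 are modelled jointly, add visit, treatment-by-visit and baseline-by-visit terms. Report the unadjusted change from baseline as a sensitivity analysis.

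No new data or visits are needed. The section already allows methods to be updated before database lock, with changes reported to the DSMB and the CF-TDN PRC. The edit is more than one added sentence, because the crossover and carryover wording has to go at the same time. The statistical cost is one degree of freedom at a single time point, and slightly more in a joint two-visit model.

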**Exclusion criteria:**

- 1) History of hypersensitivity to sildenafil
- 2) Use of an investigational agent within the 4-week period prior to Visit 1 (Day 0)
- 3) Breastfeeding, pregnant, or verbal expression of unwillingness to practice an acceptable birth control method (abstinence, hormonal or barrier methods, partner sterilization or intrauterine device) during participation in the study
- 4) History of significant hepatic (SGOT or SGPT > 3 times the upper limit of normal at screening, documented biliary cirrhosis, or portal hypertension), cardiovascular (history of aortic stenosis, coronary artery disease, pulmonary hypertension with right ventricular systolic pressure >55 mmHg or life-threatening arrhythmia), neurological (history of stroke), hematologic (history of bleeding diathesis), ophthalmologic (history of retinal impairment or non-arteritic ischemic optic neuritis) or renal impairment (creatinine >1.8 mg/dL.)
- 5) Inability to swallow pills
- 6) Previous lung transplantation
- 7) Use of concomitant nitrates,  $\alpha$ -blocker, or Ca channel blocker
- 8) Use of concomitant medications known to be potent inhibitors of CYP3A4 (e.g. ketoconazole, itraconazole, ritonavir, clarithromycin, erythromycin, rifampin, verapamil)
- 9) Presence of a condition or abnormality that in the opinion of the investigator would compromise the safety of the subject or the quality of the data
- 10) Weight less than 40 kg
- 11) History of sputum or throat swab culture yielding *Burkholderia cepacia* within 2 years of screening
- 12) History of nasal disease or nasal surgery that would, in the opinion of the investigator, impede accurate measurements of NPD
- 13) Use of anticoagulant medication (e.g. heparin, coumadin)
- 14) Resting room air oxygen saturation <93%
- 15) Use of nighttime oxygen
- 15) History of migraine headaches
- 16) Baseline BP of < 90/50 mm Hg

Study Design

This study is a randomized, placebo-controlled, double blind study of sildenafil (Revatio) in clinically stable patients with mild-moderate CF lung disease. The length of participation for each subject will be approximately 6 weeks, and will consist of a screening visit, 4 out-patient visits, and a follow-up phone assessment 2 weeks after subject's study completion.

Randomization

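### The primary and secondary endpoints are to be analysed as a 2x2 crossover with a carryover test, but each subject receives only one treatment

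*Combined protocol and SAP*

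**What the plan says.** **Design.** Under Randomization, "Subjects will be randomized in a 2:1 fashion to sildenafil or placebo". Under Dosing, each subject takes "28 days of placebo orally t.i.d. or 28 days of days of sildenafil orally t.i.d". Under Study Design, "The length of participation for each subject will be approximately 6 weeks". The visit descriptions and the Study Flowchart show screening, a Day 1 baseline, on-treatment visits at Day 8 and Day 29, and a telephone call at Day 43. NPD and sweat testing take place on Days 1, 8 and 29. There is no washout, second course or treatment sequence.

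**Analysis.** The Data Analysis section states that the primary and secondary endpoints "will be analyzed separately as a 2X2 crossover design using a repeated measures analysis". It adds "All patients will be plotted across part one and part two to discern carryover effects" and "Carryover effects in the crossover design will be fit initially but discarded if they are not (as expected) significant". If the data are non-normal, "rank based analyses (e.g. Mann-Whitney-Wilcoxon rank-sum test or other appropriate test) will be used".

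**Sample size.** The calculation is for 12 sildenafil and 6 placebo subjects. It claims 100% power for a 10.4 mV change in maximal basal PD (SD 2.59 mV) and, for sweat chloride with SD 2.6 mEq, "95% power to detect at least a 5 mEq change from placebo at the 5% significance level".

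**The concern.** A 2x2 crossover analysis estimates treatment by comparing sildenafil with placebo within the same person over two periods. Here nobody has two treatments, so the model named for the primary endpoint does not fit the data that will be collected. The analyst would have to substitute a model that the plan does not state.

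The plan also leaves the deciding visit unstated. NPD is measured after baseline at both Day 8 and Day 29. Aim 1 speaks of measurement before and after therapy, which points to Day 29, but no section says so outright. In an 18-subject trial, leaving model, contrast and visit open weakens the prespecification of the primary result.

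The carryover rule adds a further hazard. If someone made the stated model run by treating Day 8 and Day 29 as the two periods, a real difference between those visits in the effect of sildenafil, over time or after the dose step, would be tested as a nuisance term. The outcome of that test would decide what the treatment coefficient means.

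**Working it through.** **1. Timeline.** Two 28-day courses need 2 × 28 = 56 days before any washout. Stated participation is about 6 weeks, or 42 days. A second period does not fit.

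**2. The plan's own power figures.** Inputs from the Sample size section: n = 12 and 6, 5% level (two-sided assumed, since sidedness is not stated), df = 12 + 6 − 2 = 16. Let k = √(1/12 + 1/6) = 0.5. Power is from the noncentral t distribution with noncentrality δ/SE.

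| Endpoint | Design assumed | SE | δ/SE | Power |
|---|---|---|---|---|
| Max basal PD, 10.4 mV, SD 2.59 | parallel, SE = SD·k | 1.295 | 8.03 | >0.9999 |
| Sweat Cl, 5 mEq, SD 2.6 | parallel, SE = SD·k | 1.30 | 3.85 | 0.950 |
| Sweat Cl | crossover, SD is within-subject: SE = (SD·√2/2)·k | 0.919 | 5.44 | 0.9991 |
| Sweat Cl | crossover, SD is that of the period difference: SE = (SD/2)·k | 0.65 | 7.69 | >0.9999 |

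The stated 95% is the parallel-group figure. A one-sided parallel t-test gives 0.979 and a normal approximation 0.970, so neither matches. The primary endpoint's 100% holds under either design and does not tell them apart.

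**3. Estimability.** Rank of the design matrix for 18 subjects (18 subject columns plus those listed):

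| Model | Visits | Rank / columns |
|---|---|---|
| period + treatment, this trial | Days 8, 29 | 19 / 20 |
| the same plus carryover | Days 8, 29 | 20 / 21 |
| period + treatment, true 2x2 crossover | two periods | 20 / 20 |
| visit + arm-by-visit, this trial | Days 8, 29 | 20 / 20 |
| visit + treatment after baseline only | Days 1, 29 | 20 / 20 |
| visit + treatment after baseline only | Days 1, 8, 29 | 21 / 21 |

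In the first two rows treatment is a sum of subject columns and is lost. The carryover column equals arm × second visit, which is the arm-by-visit interaction. Once Day 1 is included, the between-arm difference in change from baseline is estimable.

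**4. Illustration of the carryover rule.** This applies only if Days 8 and 29 are used as periods. The Day 29 minus Day 8 difference in effect is assumed, because the documents give none. The SD of a between-visit change is taken as the protocol's 2.59 mV, so SE = 2.59 × 0.5 = 1.295 mV with df 16.

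| Assumed difference (mV) | 0.5 | 1 | 2 | 3 | 4 | 5 |
|---|---|---|---|---|---|---|
| Detected | 0.065 | 0.112 | 0.306 | 0.586 | 0.826 | 0.952 |
| Discarded | 94% | 89% | 69% | 41% | 17% | 5% |

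Detection with 80% probability needs about 3.9 mV. In a random-subject simulation (4000 runs; assumed between-subject SD 5 mV, effects 8.4 mV at Day 8 and 10.4 mV at Day 29), the treatment coefficient averaged about 8.4 with the term kept, which is the Day 8 effect. With the term discarded it averaged about 9.4, the mean of the two visits: (8.4 + 10.4)/2. The term was discarded in 68% of runs. Neither coefficient is the Day 29 change from baseline.

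**The case against.** The strongest reply is that this is leftover text in a small pilot. A repeated measures analysis can be read as arm by time; with Day 1 included, a treatment effect is estimable; the rank-sum fallback is already a two-sample test; and the plan allows its methods to be updated before database lock.

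Part of this stands. Only the within-subject sildenafil-placebo contrast is lost, not every treatment effect, and the sample size already matches parallel groups. The rest does not repair the plan. No between-arm model or deciding contrast is stated. The rank-sum test applies only if the data are non-normal, and it names no visit. The update clause is triggered by emerging data from modulator trials and NPD methodology, and it supplies no replacement model.

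It can also be said that the carryover sentence sits in a paragraph that opens with pharmacokinetics. That is so, but the only crossover design the plan names is the one for the NPD and sweat endpoints.

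Finally, the carryover figures depend on a reading the documents do not make and on assumed effects. At those assumed effects (8.4, 9.4 or 10.4 mV) a two-sample test has power above 0.9999 with SD 2.59, so the trial's conclusion would not turn on it. This is fair: the illustration shows how the rule would behave and carries no weight in the conclusion.

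**Conclusion.** The concern holds and must be fixed. The prescribed primary model contradicts the design, and its within-subject treatment effect is not estimable (rank 19 for 20 columns). The timeline (56 days needed against about 42) and the sweat chloride power (0.950 as parallel groups, at least 0.9991 as a crossover) both show that the trial was laid out as two parallel groups. These results rest on the documents' own figures and a two-sided 5% test. The data can answer the question through a between-arm comparison of change from Day 1, but the plan does not prescribe one or explicitly name the visit that decides it.

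**What to change.** Replace the crossover and carryover text in Data Analysis with one named primary test, for example:

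> Primary analysis: between-arm comparison of maximal basal PD (mean of 2 nostrils) at Visit 4 (Day 29), adjusted for the Day 1 value by ANCOVA, two-sided 5%.

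Two alternatives address the same Day 29 contrast: a two-sample test of the Day 29 minus Day 1 change, which is what the Sample size section powers, or a mixed model with baseline, arm, visit and arm-by-visit and the Day 29 contrast as primary. They can give different p-values at n = 18, so the plan should commit to one.

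Make Day 8 secondary. Keep the rank-sum test as the non-normality fallback, applied to the change. Use the same model for the other NPD measures and for sweat sodium and chloride. Delete the carryover rule and the two-part plots, and the period wording in the heading of the Day 1 visit and in the CFQ-R paragraph. Check whether the sequence number under Study Drug is also a remnant.

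The cost is protocol and SAP wording before database lock, with no extra subjects, visits or measurements. Both stated powers are unchanged for the two-sample test of change. ANCOVA spends one degree of freedom (df 15): sweat chloride power is 0.948 if the residual SD stays at 2.6, and higher if adjusting for baseline lowers that SD enough to offset the lost degree of freedom. The documents do not give the baseline correlation.

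### No single between-arm test is fixed in advance for the primary endpoint: the choice hangs on an undefined finding of non-normality

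*Combined protocol and SAP*

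**What the plan says.** All references are to the combined protocol and SAP. The Primary Endpoints list defines the endpoint as the "within subject change in maximum basal PD". Data Analysis, first paragraph, repeats it: "Primary outcome, baseline change in maximal basal PD measurement (mean of 2 nostrils), will be assessed". That paragraph then plans a 2x2 crossover, repeated-measures analysis, although Randomization and Dosing describe one 28-day treatment per subject, allocated 2:1.

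The second paragraph lets emerging outside data and newer NPD methodology change the method, log transformation included, and continues: "If these analysis suggests non-normality, rank based analyses (e.g. Mann-Whitney-Wilcoxon rank-sum test or other appropriate test) will be used". It adds a timing rule: "Any change in the statistical analysis plan will be finalized before database lock". Changes also go to the DSMB and the CF-TDN review committee.

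The third paragraph opens with pharmacokinetic data and then says: "Data will be screened for nonnormality, and appropriate transformations as needed (such as log) will be applied". It ends that route with: "Non-parametric procedures (Proc NPAR1WAY in SAS v9.2) will be applied in cases where transformations do not normalize the data". The same paragraph also covers crossover carryover and correlations that involve NPD.

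**The concern.** A confirmatory P value should come from one analysis that can be named before the data are seen. Here the second paragraph goes straight to ranks and leaves the particular test open, while the third tries a transformation first. If both govern the primary endpoint, the same data can take two routes. Nothing says how non-normality is judged, on which quantity, or by whom and whether blinded.

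The gap matters more because the default crossover model cannot be fitted to subjects who each receive one treatment. The rank-sum test, given only as an example, is then the one between-arm test named for NPD, and it is reached only through the undefined branch. At stake is which P value is reported for 18 subjects when the effect is modest.

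**Working it through.** **Inputs.** 12 sildenafil and 6 placebo; 10.4 mV; SD of change 2.59 mV; 5% level (Sample size: "Based on a 2.59 mV standard deviation of the change in conductance of the maximal basal PD with placebo" and "enrollment of 12 (sildenafil) and 6 (placebo) subjects will provide 100% power to detect a 10.4 mV change in maximal basal PD"). Two-sided testing is assumed, since sidedness is not stated.

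**The plan's own figure.** Standard error = 2.59 × √(1/12 + 1/6) = 2.59 × 0.5 = 1.295 mV. Noncentrality = 10.4 / 1.295 = 8.03 on 16 df. Two-sample t power exceeds 99.99%, so the stated 100% reproduces. The planned effect is 10.4 / 2.59 = 4.0 SD. Power of 80% is reached at 3.86 mV, that is 3.86 / 2.59 = 1.49 SD.

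**Simulation.** 12 versus 6, pooled t-test against exact rank-sum test. The screen is Shapiro-Wilk at 5% on within-arm residuals. The screen, its cut-off and the error distributions are assumptions, because the plan names none. The t-test stands in for the crossover model. There were 20,000 trials per scenario at 0 and 1.49 SD, and 10,000 at 1 and 4.0 SD.

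| Errors | Screen flags (no effect) | Type I error, screen then test | Tests disagree, 1 SD | 1.49 SD | 4.0 SD |
|---|---|---|---|---|---|
| Normal | 4.8% | 4.9% | 10% | 7.8% | 0.0% |
| t(3) | 27% | 5.4% | 12% | 8.0% | 0.3% |
| Lognormal, sigma 0.5 | 39% | 4.9% | 11% | 9.1% | 0.1% |
| Exponential | 64% | 5.2% | 13% | 10.2% | 0.2% |
| Lognormal, sigma 1 | 80% | 4.7% | 17% | 10.2% | 0.9% |

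Reporting whichever of the two tests is significant gives a type I error of 5.4% to 5.9%.

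**What is screened matters.** With perfectly normal errors at the planned 4.0 SD effect, the screen flags about 43% of samples when the arms are pooled, but about 5% when within-arm residuals are used. The pooled sample is a mixture of two separated groups, so the treatment effect itself looks like non-normality. With exponential errors at 1.49 SD the error goes the other way: the pooled screen flags 19% and the residual screen about 64%.

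**Log.** A signed change has no log when it is negative. If placebo changes are symmetric about zero (assumed), all six are positive with probability 0.5^6 = 1.6%. With no effect, all 18 are positive with probability 0.5^18 = 0.0004%. Taking logs of PD magnitude at each visit and then differencing is computable where the PDs share a sign, but it estimates a ratio. The sample size is based on a difference in mV.

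**The case against.** The strongest defence has four parts.

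- **Scope.** A reader might infer that the two paragraphs contradict each other outright. The documents do not establish that: the third opens with pharmacokinetic data, and its screen may be meant for those alone. Both routes can also end at the same rank-sum test. What stands is that the later carryover and NPD sentences leave the scope unclear.
- **Source of the finding.** A reader might infer that a screen of this trial's 18 subjects certainly picks the primary test. The sentence follows one about outside trials and may refer to those data. On that reading, outside evidence picks the test by no stated criterion, so the test is still open.
- **Timing.** A reader might infer that the rule on finalising changes before lock cannot be met. It can: the trial is double-blind, a pooled look before lock is possible, and following a branch already written is not a change of plan. But a pooled look confuses effect with shape, as shown above.
- **Log.** A reader might infer that the log remedy is impossible. Neither paragraph says that the change itself is logged, so the 1.6% and 0.0004% figures apply only if it is. The shift from a difference to a ratio remains.

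It is also fair that a mechanically applied screen does little damage to overall error rates, so its low sensitivity is not in itself a large fault.

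**Conclusion.** The point holds in limited form. The primary test is not fixed, because the trigger is undefined, the fallback is open-ended, a second route may or may not apply, and the default model does not fit the design.

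The size is modest. Across the five distributions assumed, the screen-then-test procedure has type I error of 4.7% to 5.4%. At 10.4 mV the two tests disagree in under 1% of trials. The room for choice lies at smaller effects: opposite verdicts in roughly 8% to 13% of trials at 1 to 1.5 SD (about 2.6 to 3.9 mV), and 17% for the most skewed errors at 1 SD. Large inflation of type I error might be inferred, but the calculations do not support it. These sizes rest on the assumed screen, distributions and stand-in t-test. The gap in pre-specification rests on the text alone.

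**What to change.** In Data Analysis, replace the crossover model for the primary endpoint with one named analysis for the parallel 2:1 design: the between-arm difference in change in maximal basal PD, in mV, with the Day 1 value as covariate. A randomisation P value is optional; if used, it should follow the actual allocation scheme.

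Then:
- remove the normality screen and the log option for this endpoint;
- always run the rank-sum test, labelled as a sensitivity analysis;
- state which data the screen-and-transform rule in the third paragraph covers;
- require any change of method to be final before outcome data are seen by arm.

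The cost is SAP wording and a few lines of code, with no extra subjects, visits or measurements. The downside is some power lost to the rank test if changes are strongly skewed: in the simulation at 1.49 SD with lognormal (sigma 1) errors, 86% for the t-test against 92% for rank-sum. With normal errors the order reverses, 80% against 74%.
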